The Nellix System was designed to withstand the migration and lateral displacement forces acting on endografts, while at the same time excluding the aneurysm sac lumen and minimizing endoleaks of any kind. The system is comprised of two independent flow channels, one to each iliac artery. Each flow channel consists of a balloon-expanded ePTFE covered stent surrounded by a Polymer-filled EndoBag which fills the blood lumen within the aorta, thus providing positional stability of the endograft and sealing the aneurysm completely from side-branch flow.[§] A clinical trial has been performed to assess the safety and effectiveness of the first generation Nellix system for endovascular AAA repair and results serve as the basis for CE Mark approval (October 2012); initial results to one year have been reported.^{**} Results of this trial demonstrate the versatility of the Nellix System in treating a variety of AAA anatomies, including those that have common iliac artery involvement bilaterally.

Continued clinical evaluation of the Nellix System in a broader group of institutions and physicians is therefore appropriate to assess the safety and effectiveness of the device for AAA repair and the generalizability of the approach.

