6.3. ADDITIONAL EVALUATIONS

Additional evaluations include:

- **Procedural and In-Hospital Evaluations:**
 - Volume of contrast media used;
 - Fluoroscopy time;
 - Total procedure time;[‡]
 - Time in ICU;[§]
 - Estimated blood loss;
 - % requiring blood transfusion;
 - Anesthesia time;[¶]
 - Time to hospital discharge;[£]
- **Mortality**, all-cause and aneurysm-related, within 30 days, at 6 months, and annually to 5 years;
- **MAE Individual Components** within 30 days, at 6 months, and annually to 5 years;
- **Composite MAEs** after 30 days, at 6 months, and annually to 5 years;
- **Aneurysm Rupture** within 30 days, at 6 months, and annually to 5 years;
- **Conversion to Open Surgical Repair** within 30 days, at 6 months, and annually to 5 years;
- **Adverse Events** (serious and non-serious) within 30 days, at 6 months, and annually to 5 years;
- **Device Performance** (aneurysm sac diameter change from the first post-operative visit; device migration; clinically significant device migration, incidence of endoleak) at 30 days, 6 months, and annually to 5 years;
- **Renal Function** pre-discharge and at 30 days, 6 months, and annually to 5 years, as assessed by the estimated glomerular filtration rate (eGFR) and changes over time;
- **Device Patency and Integrity** within 30 days, at 6 months, and annually to 5 years, as determined by contrast-enhanced CT scan, and as assessed by the independent core laboratory, inclusive of:
 - Patent luminal flow
 - Absence of kinking or occlusion
 - Absence of stent fracture
 - Absence of device failure
- **Luminal Thrombus Requiring Intervention** within 30 days, at 6 months, and annually to 5 years;
- **Secondary Procedure** within 30 days, at 6 months, and annually to 5 years for resolution of endoleak, device occlusion, migration, aneurysm sac expansion and/or a device defect.

[‡]Elapsed time from the first break of skin to final closure (i.e., skin to skin time).

[¶]Elapsed time from the initiation to the end of the anesthesia protocol.

[§]Elapsed time from the first administration of anesthesia to release from the ICU or post-anesthesia care unit providing ICU-level care. If the patient is not admitted to the ICU, this is defined as 0 hours.

[£]Elapsed time from initiation of the procedure to physical discharge from the hospital.

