8.8.4. Secondary procedures

For subjects that experience any non-diagnostic invasive secondary treatment of the groin access

Confidential. This document and the information contained herein may not be reproduced, used or disclosed without written permission from Endologix, Inc.

areas or of the abdominal aortoiliac vessels (e.g., hematoma drainage, vascular exploration for bleeding, iliac stenting, thrombectomy, additional device placement for endoleak, embolization for Type II endoleak, conversion to open repair, etc.), it is important to identify the specific procedure performed on the relevant **ADVERSE EVENT** eCRF. A copy of the discharge summary source document should be uploaded to the EDC system.

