- *Clinically significant migration*: Core Lab reported stent distal movement >10mm from the original implant location relative to the center of the distal renal artery resulting in an intervention or in a serious complication.
- *Occlusion*: Intervention for stent occlusion or as reported by the Core Lab.
- *Secondary procedure*: any non-diagnostic intervention after the index procedure intended to correct or repair an endoleak, device occlusion, migration, aneurysm sac expansion and/or a device defect (including infection).

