- *Secondary Endovascular procedures:* A descriptive analysis of secondary endovascular procedures for resolution of endoleak (Type I or III), device occlusion, migration, aneurysm sac expansion, and/or a device defect (including infection) will be done at 30 days and at each subsequent time point for which data are available.

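### The secondary-procedure analysis in section 10.8 is narrower than the measure defined in 6.3 and 8.8.7: it leaves out procedures done solely for a Type II (or Type IV) endoleak, and open procedures that are not conversions.

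*Combined protocol and SAP*

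**What the plan says.** Four current texts describe the same evaluation.

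- **Section 10.8 (analysis).** It plans "A descriptive analysis of secondary endovascular procedures for resolution of endoleak (Type I or III), device occlusion, migration, aneurysm sac expansion" and device defect (infection included), which "will be done at 30 days and at each subsequent time point for which data are available". Follow-up runs to five years.
- **Synopsis, Additional Evaluations.** It has the same Type I or III limit, but counts open surgery as well as endovascular procedures.
- **Section 6.3 (list of evaluations).** It lists secondary procedures within 30 days, "at 6 months, and annually to 5 years for resolution of endoleak, device occlusion, migration, aneurysm sac expansion and/or a device defect". Neither the endoleak type nor the approach is restricted.
- **Section 8.8.7 (definition).** A secondary procedure is "any non-diagnostic intervention after the index procedure intended to correct or repair an endoleak, device occlusion, migration, aneurysm sac expansion and/or a device defect". The endoleak definition in the same section includes Type II (patent collateral vessel) and Type IV (trans-device).

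Section 8.8.4 tells sites to identify invasive secondary treatments on the Adverse Event eCRF, and one of its examples is "embolization for Type II endoleak".

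**The concern.** A subject can have a secondary procedure by the protocol's definition and still be absent from the planned analysis of secondary procedures. Two analysts who each follow the protocol could report different rates from the same data, one from 8.8.7 and one from 10.8. The analysis section is the one likely to be programmed, and it gives the smaller number.

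Re-intervention over five years is a central descriptive outcome for an endovascular device. Section 4.2 says that endoleaks after stent-graft repair are mostly Type II, that endoleaks may require re-intervention, and that such procedures add risk and cost. It describes this device as "sealing the aneurysm completely from side-branch flow". How often Type II leaks needed treatment is therefore of interest here, and no planned table shows it.

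**Working it through.** The documents state no expected secondary-procedure rate, so there is no figure to reproduce. The check compares the texts and then works out the effect per subject.

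**Step 1. Scope of each text.**

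| Source | Endoleak types | Approach |
|---|---|---|
| 8.8.7 definition | any | any non-diagnostic intervention |
| 6.3 | any | not restricted |
| Synopsis | I or III | endovascular or open |
| 10.8 | I or III | endovascular only |

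All four also list occlusion, migration, sac expansion and device defect. They differ on two points: endoleak type (8.8.7 and 6.3 against the synopsis and 10.8) and approach (10.8 against the other three).

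**Step 2. Who is counted.** Take subjects with a single secondary procedure.

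| Procedure | 8.8.7 and 6.3 | Synopsis | 10.8 |
|---|---|---|---|
| Endovascular, for Type I or III endoleak | yes | yes | yes |
| Endovascular, for Type II endoleak, indication includes sac expansion | yes | yes | yes |
| Endovascular, for Type II or IV endoleak only, no sac expansion | yes | no | no |
| Open, for example for device occlusion, not a conversion | yes | yes | no |

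The last two rows are what 10.8 loses. A subject who also has a procedure that 10.8 counts remains in a subject-level rate.

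**Step 3. Whether another 10.8 item fills the gap.**

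- Incidence of Endoleak covers every type at each follow-up, but counts leaks, not treatments.
- Conversion to Open Repair captures conversions, but not embolizations or other open procedures.
- Luminal Thrombus Requiring Intervention is limited to endovascular surgical intervention for thrombosis.
- The serious and non-serious adverse event proportions have no breakdown by procedure or cause.

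None gives the missing counts.

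**Step 4. Effect per subject.** Let *N* be the subjects evaluated, *a* those counted under 10.8, and *k* those counted under 8.8.7 but not under 10.8.

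Difference = (a + k)/N − a/N = k/N.

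- N = 150 (maximum pivotal cohort, section 5.1), k = 1: 1/150 = 0.67 percentage points.
- N = 132 (one-year sample size, section 10.7.2), k = 1: 1/132 = 0.76 percentage points.

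The documents give no value for *k*. As an assumption made only to show scale, k = 3 of 150 is 2 points and k = 15 of 150 is 10 points. Nothing in the documents places *k* within that range.

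**The case against.** The strongest reply is that this is a wording mismatch in one descriptive evaluation, with little lost.

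- **Type II leaks are still reported.** A reader might infer that the restriction removes the evidence on whether the device seals off side-branch flow. The documents do not support that. Section 10.8 presents endoleak of any type, new and persistent, at each follow-up, together with sac diameter change. Those are more direct evidence than a procedure count, which also depends on decisions to treat. Only the re-intervention part is missing.
- **Not every Type II re-intervention drops out.** Section 10.8 keeps procedures for sac expansion whatever the leak type. The loss is confined to procedures with no other listed cause.
- **The size is unknown.** A reader might take the statement in section 4.2 that more than 25% of subjects develop an endoleak as a guide to the number omitted. That figure concerns leaks, not procedures, and stent-graft repair in general, not this device.
- **Section 8.8.4 does not define the rate.** It is a data-capture instruction that also lists groin procedures outside 8.8.7. It shows that the data will exist, not that Type II embolization was meant to be in the analysed rate.
- **The narrow version may be the intended one.** The synopsis, 10.8 and every statement of the primary endpoint use Type I or III, so the untyped wording in 6.3 could be the drafting slip.

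All five points stand as limits on the claim, but none removes the contradiction. If the narrow version was intended, 6.3 and 8.8.7 need correcting instead.

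**Conclusion.** The inconsistency is real and lies in current text. As written, section 10.8 does not report the measure that 8.8.7 defines and 6.3 lists. It omits subjects whose only secondary procedure was for a Type II or Type IV endoleak without sac expansion. It also omits open secondary procedures, apart from those that appear separately as conversions to open repair.

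The size is 0.67 percentage points per omitted subject at N = 150, and more at later visits with fewer subjects evaluated. This assumes a subject-level proportion, which 10.8 does not specify. The total is not known.

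The effect stops at this descriptive evaluation. The synopsis, 6.2 and 10.7.2 all limit the endoleak components of Treatment Success to Type I or III, so the primary test and its sample size are unaffected. A reader might infer that effectiveness is overstated; the documents do not support that. The point is worth correcting because two five-year rates can be drawn from the same data and the plan does not say which is meant.

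**What to change.** Reconcile the synopsis, 6.3, 8.8.7 and 10.8 to one definition of secondary procedure, settling both endoleak type and approach.

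In 10.8, report all secondary procedures that meet 8.8.7. Tabulate them by cause (endoleak by type, occlusion, migration, sac expansion, device defect) and by endovascular or open approach. Give the Type I/III subset as a separate row, so that both rates stay visible whichever was intended. State whether the unit is the subject or the procedure, and how a subject with several causes is counted. Leave the primary endpoint as it is.

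The cost is protocol and SAP wording and a few table rows. Section 8.8.4 already asks sites to identify the specific procedure, so no new data collection is needed. The reported rate may look less favourable.

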10.9 CONTINUED ACCESS

Data collected from patients enrolled in the Extended Investigation (continued access) phase will be evaluated separately from that of the Primary Investigation. No formal hypothesis testing will be performed in this separate continued access cohort. Only descriptive statistics will be presented on this cohort.

11. ADMINISTRATIVE PROCEDURES

11.1 STATEMENT OF COMPLIANCE

This clinical investigation will follow the international standard for Clinical Investigation of Medical Devices for Human Subjects -- Good Clinical Practice (ISO 14155:2011). The Sponsor and Investigator(s) will comply with their responsibilities as defined in 21 CFR 812.

11.2 RESPONSIBILITIES

1. *Sponsor:* Endologix is responsible as the Sponsor to ensure proper site and investigator selection, availability of signed investigator agreements prior to study initiation, availability of regulatory and EC/IRB approval prior to the initiation of the study at any site, obtaining and maintaining appropriate insurance policies for the study, and management and monitoring of the study with special attention to verification of all clinical requirements, adherence to protocol, good clinical practices and compliance with applicable government and institutional regulations. Furthermore, the sponsor is responsible for ensuring proper regulatory approvals are obtained, and reporting to regulatory authorities per applicable regulations.
2. *Investigators:* Each investigator and study site is required to conduct the clinical investigation in accordance with the protocol, the signed investigator agreement, Good Clinical Practices (GCP), all applicable laws and regulations and any conditions or restrictions imposed by the reviewing EC/IRB. This includes compliance with requirements related to EC/IRB approval and reporting, and proper patient informed consent prior to participation in the study. The investigator is also responsible for protecting the rights, safety, and welfare of the subjects under his or her care.
 - a. Each investigator is responsible for supervising all procedures conducted under this protocol at his or her institution.
 - b. Furthermore, the investigator is responsible for ensuring that data are completely, accurately, and promptly entered in each patient's eCRFs and related documents are

available to verify the accuracy of the eCRFs, and for ensuring the clinical monitor has access to all necessary records to ensure the integrity of the data.

3. *CT Scan Core Laboratory*: The CT Scan Core Laboratory is a contract supplier having validated processes that is responsible for receipt, de-identification, handling, processing, and assessment of all submitted CT scans preoperatively and postoperatively and for reporting of results per a written, approved protocol.
4. *Data Management Group*: The data management group is responsible for electronic data capture database development, validation, control and management of input from study sites/monitored data, maintenance, and reporting for statistical analysis.
5. *Clinical Events Committee*: The independent clinical events committee will consist of at least three physician members and is responsible for review of events and complications documented on the eCRFs and in source documents by the study PIs during the trial, and for categorization of these events according to the event definitions and primary endpoint criteria in this protocol. An independent clinical safety review will examine all AEs and SAEs. MAEs will undergo adjudication by the CEC panel. Reviews will occur on an ongoing basis throughout the trial as events are reported. The adjudicated events will be reviewed by the Data Safety Monitoring Board.
6. *Data Safety Monitoring Board (DSMB)*: Consistent with the U.S. FDA guidance document *Establishment and Operation of Clinical Trial Data Monitoring Committees*, Endologix has established a DSMB having pertinent expertise to review on a regular basis adjudicated safety data accumulated and trial progress (i.e., enrollment among groups; completeness and timeliness of data; protocol deviations; etc.) from its ongoing clinical investigations. The DSMB consists of five members, two of which must be physicians with specialty training in endovascular repair. One member of the DSMB is a statistician. The DSMB will be convened to review interim data accumulated during the trial and to render a recommendation for enrollment in the trial: continue; amend; suspend; or, terminate. All action items discussed during the meeting will be documented in the minutes, with agreed upon target completion dates for resolution. The final meeting minutes will be distributed to all DSMB members. Endologix will disclose the recommendations of the DSMB to the US FDA in its annual progress reports to the IDE.
7. *Independent Reviewer*: The Independent Reviewer will be an expert in endovascular therapy for repair of abdominal aortic and aortoiliac aneurysms. The Independent Reviewer will review all aneurysm-related images prior to subject enrollment into the study. Approval by the Independent Reviewer will include assessing vascular suitability for treatment with the study device and review of anatomic measurements provided by the Core Lab to determine each patient's eligibility. More than one Independent Reviewer may be required for case selection decision adjudication.
8. *Biostatistician*: The biostatistician is responsible for the development and implementation of the data analysis plan, for conducting the data analysis, and for reporting it per the plan.

11.3 PATIENT PROTECTION

This clinical investigation will be conducted in accordance with the ethical principles that have their

Confidential. This document and the information contained herein may not be reproduced, used or disclosed without written permission from Endologix, Inc.

origin in the Declaration of Helsinki. Written informed consent, in accordance with applicable international and local study center regulations, must be obtained from each patient, or from their legal representative, prior to the formal screening process as outlined in this protocol. The PI will retain a copy of the signed informed consent document in each subject's record, and provide a copy to the subject. The PI will not request the written informed consent of any patient, and will not allow any patient to participate in the investigation before obtaining EC/IRB approval.

Attachment 2 provides a sample of the consent form that may be used for the study. The sample contains the minimal consent language content that must be incorporated into the Informed Consent Document. Other elements or language may be added, or minor edits to the language may be made, but no substantial content may be deleted.

Prior to starting the study, the PI will provide Endologix with a copy of the sample Informed Consent Document approved by the EC/IRB with documented evidence that the EC/IRB has approved the protocol.

Appropriate precautions will be taken to maintain confidentiality of patient medical records and personal information. However, the patient's name may be disclosed to the sponsor or designee, or any health authorities if they inspect the study records. A report of this study may be published; however the patient's identity will not be disclosed.

11.4 PROTOCOL CHANGES

The PI should not implement any deviation from or changes to the protocol without approval by Endologix and prior review and documented approval from the governing EC/IRB. The only exception to this is where necessary to eliminate immediate hazards to study subjects, or when changes involve only administrative aspects (e.g., change in monitors, telephone numbers, etc.).

A report of withdrawal of EC/ IRB approval must be submitted to the Sponsor within five working days.

11.5 DOCUMENTATION

Clinical Investigator's Brochure: Prior to or at the time of training for the study, the PI will be provided with a Clinical Investigator's Brochure (CIB). This document serves as a briefing document to provide reports of prior investigations regarding nonclinical and clinical safety and effectiveness studies, as well as published and unpublished information for reference and review.

Source Documents: Source documents may include a patient's medical record, hospital charts, clinic charts, the investigator's study files, questionnaires, as well as the results of diagnostic tests such as laboratory tests, CT scans, angiograms, and the like. Source document worksheets will be provided by Endologix for use by study personnel.

The following information should be included in the patient's medical record:

- Patient's name and contact information;
- The study title, number/name, and sponsor name;

Confidential. This document and the information contained herein may not be reproduced, used or disclosed without written permission from Endologix, Inc.

- The patient ID number;
- A statement that written informed consent was obtained;
- Date of procedure and implanted device information;
- Dates of all visits;
- Occurrence of complication and adverse events, hospitalizations, or adverse events;
- Date patient exited the study, and a notation as to whether the patient completed the study or discontinued, with the corresponding reason.

Electronic Case Report Form Completion: The PI who signs the protocol signature page must personally electronically sign the eCRFs to ensure that the observations and findings are entered correctly and completely. The eCRFs are to be entered in a timely manner at the intervals specified by Endologix and this protocol.

All eCRFs must be entered as instructed. An explanation must be provided for any missing data points. Completion instructions and training will be provided to each site for reference.

All eCRFs will be reviewed and monitored for completeness and clarity. Queries for missing or unclear data will be made as necessary throughout the study. Timely resolution of queries is required by institutional staff and the PI.

Study Logs: The following logs will be maintained for the study:

- Investigator and site training to the protocol (Training Log)
- Authorized study site personnel (Site Signature Log)
- Patient consent and screening (Enrollment Log)
- Monitoring visit tracking (Site Visit Log)
- Nellix Inventory eTracking Log (Device Accountability Log)

Document Retention: Study-related correspondence, patient records, consent forms, records of device implant, and source documents are to be maintained by the study site. Endologix requires that it be notified in writing if the PI wishes to relinquish ownership of the data and information so that mutually agreed upon arrangements can be made for transfer of ownership to a qualified entity.

Publication: Endologix, as the sponsor of record, has a proprietary interest in this study. Authorship and manuscript composition will reflect joint cooperation between multiple investigators and sites, core laboratories, and Endologix. Authorship will be established prior to writing of the manuscript. No individual publications will be allowed prior to the completion of the final report for this study and as agreed in writing by Endologix.

